There remains a lack of prospective and controlled research on the behavioral, toxicological, and physiological effects of electronic cigarettes (ECs) to help the public health community come to a clear and accurate consensus on their risk-benefit. Moreover, the studies that have been completed used various commercially available ECs, e-liquid flavors, and nicotine concentrations, many of which are unavailable today and for which we know very little about, making the generalizability and comparisons between past, present, and future studies very difficult. The present funding opportunity (PAR-17-156) is meant to begin to evaluate, with a high degree of fidelity, ECs as a potential means of reducing smoking-related risks and to provide information on the use and effects of JUUL; it is also meant to do so quickly (two-year study). In order to successfully execute the proposed study, we plan to recruit and enroll recent smoking cessation treatment failures from a state quitline (QL), which predominately serves priority populations (e.g., low socioeconomic status, high levels of mental health conditions). QLs provide ready access to a large number of tobacco users, as well as infrastructure for delivering and testing study interventions quickly. With a two-year time window, QLs are potentially the best real-world platform to quickly and with sufficient statistical power, meaningfully examine smokers' ability and willingness to switch to JUUL, and its impact on their tobacco use behaviors, nicotine dependence, and health. The proposed study will randomly assign 420 smokers who were recent QL treatment failures to JUUL or combination nicotine replacement therapy (NRT). All participants will receive three calls from QL coaches. JUUL and NRT will be provided at no cost for 8 weeks, and the final follow-up will occur 12-weeks post baseline. Our specific aims are to evaluate 1) provision of JUUL vs. NRT on product switching/substitution, craving/withdrawal, abuse liability, number of cigarettes smoked, and perceived nicotine dependence; 2) changes in carbon monoxide (iCO), a biomarker of tobacco constituent exposure; and 3) which EC device characteristics and effects (e.g., satisfaction, "throat hit", craving reduction) influence complete (vs. partial or no) switching.

Project Narrative/relevance to public health:

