The purpose of the present funding opportunity (PAR-17-156) is to begin to evaluate, with a high degree of fidelity, ECs as a potential means of reducing smoking-related risks and to provide information on the use and effects of JUUL; it is also meant to be completed quickly (two-year study). In order to successfully execute our research plan, we will conduct the present study with a quitline (QL) population, characterized by high levels of nicotine dependence, low socioeconomic and educational attainment, and high levels of substance use and mental health disorders—priority populations for tobacco control. QLs provide ready access to a large number of tobacco users, as well as infrastructure for delivering and testing study interventions. Our team has successfully carried out large-scale QL recruitment (e.g., 2,000 smokers in 8 months) for past trials. QLs are potentially the best real-world platform to quickly and with sufficient statistical power, meaningfully examine smokers' willingness to switch to JUUL and its downstream effects on smoking and health.

Therefore, the overall aim of the proposed study is to evaluate the provision of JUUL versus NRT on smoking behavior, product use patterns and continued use, and iCO, a biomarker of toxicant exposure, among a sample of recent QL treatment failures. We will randomly assign 420 smokers to JUUL or treatment as usual, combination nicotine replacement therapy control (NRT). All participants will receive three calls from QL coaches and JUUL and NRT will be provided at no cost for 8 weeks. The final follow-up will occur 12-weeks post baseline.

Aim 1: To assess JUUL vs. NRT on product switching/substitution, craving/withdrawal, abuse liability, number of cigarettes smoked, and perceived nicotine dependence. *Hyp 1a: Complete product substitution (vs. partial or no substitution) will occur at a significantly higher rate among smokers randomized to the JUUL compared to those randomized to NRT at 8 and 12-week follow-ups. Hyp 1b: Compared to those randomized to NRT, JUUL participants will report less nicotine craving, fewer nicotine withdrawal symptoms, smoke fewer cigarettes per day, and higher perceived nicotine dependence.*

Switching to a Vaping Device: Evaluating Risk Reduction among Quitline Treatment Failures

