State QL registrants who have recently failed quitting smoking using the standard quitline program will be screened for potential eligibility in the present study (n=420) by Optum or OSU research staff. Potential participants, who enrolled in quitline treatment 4-6 months prior, will be recruited during proactive calls by Optum or OSU research staff or online screener via REDCap. Optum or OSU staff will screen, consent and complete baseline measures over the telephone or online via REDCap. Randomization will be stratified by sex, location, educational attainment, and ever use of ECs. Participants who meet the following eligibility criteria will be invited to participate in the study. Inclusion criteria: 1) Smoke, even a puff, within the past 24 hours; 2) currently smoke ≥ 5 cigarettes per day; 3) read, write, and speak in English; 4) report at least minimal interest in switching to an alternative nicotine delivery product (> "not at all" on a Likert-type scale); 5) enrolled in the state tobacco quitline within the last 4-7months; and 6) valid mailing address. Exclusion Criteria: 1) Currently enrolled in a contradictory study (Project ENDSmoking Study, the American Indian/Alaskan Native program, or the Pregnancy Quitline program); 2) cohabitates with a currently enrolled participant in the REACH study; 3) <21 years old; 4) current daily use of an e-cigarette over the last month; 5) change in activities or taking medication to treat a rapid or irregular heartbeat or serious or worsening angina or heart pain in the past 6 months; 6) had a heart attack or stroke/TIA within the last six months; 7) current diagnosis of bipolar disorder, or schizophrenia or hospitalization in the past year for psychiatric condition (past and current stable conditions will be allowed); 8) reaction to using patch medication or adhesive tape that resulted in a rash or hives, swelling of face or throat, wheezing or shortness of breath, or high fever or skin irritation that continued despite moving patch medication or adhesive tape to a difference site and/or using hydrocortisone cream; 9) known allergy to propylene glycol or vegetable glycerin; and 10) currently pregnant, planning to become pregnant within the next 3 months, or breastfeeding.

Recruitment Feasibility and Retention

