Recruitment: We intend to enroll 420 participants over an 12-month period (out of 24 months: 6 months for planning and Optum technology application changes, 12 months for recruitment, 3 months for final follow-up, and 4 months for data cleaning/analysis). Estimating based on FY16, the total number of QL registrants over the study period will include $\sim 74,000$ smokers ($\sim 3,000$ registrants per month). Assuming a 30% abstinence rate, our pool of potential participants is 51,800 ($74,000 \times .70$). Because we are trying to recruit 420 participants (0.7% of our potential pool) over a 12-month period, we are confident that our recruitment approaches will yield sufficient numbers and in our ability to recruit ~ 31 smokers per month (420/12 months). Moreover, [name] (Co-I) and research scientists from Optum conducted a randomized controlled trial with the OKHL and successfully screened, recruited and enrolled 2000 smokers in eight months (Bush 2008, Bush 2012, [name] 2015), lending further credibility to our methods, team, and ability to recruit sufficient numbers for the present study.

Retention: All participants who complete baseline and follow-up self-report assessments by phone will receive \$25 per assessment (up to \$75), and up to \$255 for completing daily EMAs over the 12-week study period for a total of \$330. For daily surveys (2 per day) and breath tests completed, participants can earn based on a percentage of completion. Completion of 50-79% will earn \$45, 80-89% will earn \$70, and $\geq 90\%$ will earn \$85 at the Week 4, Week 8, and Week 12 study periods, up to \$255 during the 12-week active study period for

Switching to a Vaping Device: Evaluating Risk Reduction among Quitline Treatment Failures

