TLFB		x	x	Cigarette/Vape Availability
Motivation Rulers – 8 to 12		x	x	Cessation Motivation
Cigarette Purchase Task		x	x	Smoking Restriction
iCO		x	x	Vaping Restriction
				Cigarette Reward Value
				Alcohol Use

* Daily Diary EMAs also include Random EMA items

E. Statistical Methods

1. Power Analysis

Complete substitution of combustible cigarettes for EC products is the primary outcome of the study, as the rate of product substitution will likely drive the outcomes for all of the other aims. We will compare the proportion of participants with complete substitution in the JUUL vs. NRT at the end of the product trial phase (8-week follow-up) using the Fisher's exact test. There are no direct data available on which we can base sample size estimates for the proposed study. The closest estimate for the JUUL arm was based on the 6 week, 35% switch rate for JUUL in a pilot study of a community sample of African American/Black smokers ([name], personal communication). Likewise, we estimate that the percent of complete substitution will be 35%. For the NRT, the closest estimate was the 4 week, 30% abstinence rate for preferred NRT product among a sample of smokers motivated to quit smoking¹⁵⁶; however, we will conservatively assume a NRT substitution rate of 20% since participants will have tried NRT previously and were not successful. We will assume an attrition rate of 20%. Assuming 20% attrition among a total of 420 participants (186/group), will allow 300 participants to be analyzed in the final sample. A sample size of 300 will provide >80% power to detect a difference in complete substitution between JUUL and NRT groups for a two-sided .05 level chi-squared test. It is important to note that this sample size is deliberately conservative, as it does not assume the availability of repeated outcome measures that will be taken throughout the study. By choosing models that utilize longitudinal data, we will further increase the power to detect differences between arms

2. Data Analytic Plan

Statistical analyses will be performed using SAS 9.4. P-values less than .05 will be considered statistically significant. Baseline demographics and smoker characteristics will be summarized by groups (JUUL and NRT), as appropriate. Continuous variables will be presented as mean \pm SD and compared among the 2 groups using ANOVA test. Categorical variables will be presented as counts and proportions and compared among the 2 groups using the chi-squared test.

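### The sample-size sentence contradicts itself: 420 randomised gives neither 186 per group nor 300 analysed at 20% attrition

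*Combined protocol and SAP*

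**What the plan says.** Section E.1 (Power Analysis) puts the randomised total, the per-group number, the attrition rate and the analysed number into one sentence: "Assuming 20% attrition among a total of 420 participants (186/group), will allow 300 participants to be analyzed in the final sample". It then claims more than 80% power at 300 analysed, using a two-sided 5% chi-squared test. The section assumes 35% complete substitution with JUUL. For NRT it cites a 30% four-week abstinence rate as the closest estimate, then departs from it: "we will conservatively assume a NRT substitution rate of 20% since participants will have tried NRT previously". Earlier in the same section, the arms are to be compared "at the end of the product trial phase (8-week follow-up) using the Fisher's exact test", so the test named for the comparison is not the test used for the power claim.

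The total of 420 is stated consistently elsewhere:
- Abstract: "The proposed study will randomly assign 420 smokers who were recent QL treatment failures".
- Section A (Specific Aims): "We will randomly assign 420 smokers to JUUL or treatment as usual".
- Section D.2 (Participant Screening and Randomization): "will be screened for potential eligibility in the present study (n=420").

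Section D.2 (Recruitment Feasibility and Retention) uses 420 as well, but derives from it "31 smokers per month (420/12 months") and "420 participants (0.7% of our potential pool"), with a pool of 51,800.

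**The concern.** This is the only sample-size justification for the primary outcome, and its figures exclude one another. A reader cannot tell whether the plan commits to 336 or 300 analysed participants. If the trial randomised 420 and ended with 300, that would match the stated analysed number but breach the stated attrition assumption. The recruitment section carries the same inconsistency into the feasibility argument, where the required monthly intake for 420 is understated by 4 (31 instead of 35) over a fixed 12-month window.

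The word *conservatively* is a secondary matter. In a superiority comparison where JUUL is expected to do better, a lower control rate enlarges the assumed effect. Readers are told that the NRT assumption is cautious when it is the choice that makes the required sample small.

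**Working it through.** **Inputs.** From E.1: total 420, 186 per group, attrition 20%, 300 analysed, JUUL 35%, NRT 20% (cited source 30%), two-sided 0.05. From D.2: 12 months of recruitment and a pool of 74,000 × 0.70 = 51,800. Equal allocation is an assumption; no ratio is stated, but a single per-group figure implies it.

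**1. The plan's power claim, taken alone.** With 150 analysed per arm, the pooled-variance normal approximation is

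power = Φ{ [ |p₁ − p₂|√n − 1.96√(2p̄(1 − p̄)) ] / √(p₁(1 − p₁) + p₂(1 − p₂)) }, with p̄ = 0.275.

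Putting the numbers in: (0.15 × 12.247 − 1.96 × 0.6315) / 0.6225 = 0.963, and Φ(0.963) = 83.2%. Summing the two binomial distributions over all outcomes that the test rejects gives exact power of 83.5% for chi-squared and 80.3% for Fisher's exact test. The claim of more than 80% at 300 analysed therefore reproduces.

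**2. The sample-size sentence and the recruitment figures.**

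| Quantity | Stated | From a total of 420 | From a total of 372 (186 × 2) |
|---|---|---|---|
| Per group | 186 | 420/2 = 210 | 186 |
| Analysed at 20% attrition | 300 | 420 × 0.8 = 336 | 372 × 0.8 = 297.6 |
| Recruits per month | 31 | 420/12 = 35 | 372/12 = 31 |
| Share of pool | 0.7% | 420/51,800 = 0.81% | 372/51,800 = 0.72% |

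All four derived figures fit 372, the analysed number by rounding, and none fits 420. Other routes do not reconcile them:
- 300 analysed out of 420 would be 1 − 300/420 = 28.6% attrition.
- 300/0.8 = 375.
- 300 × 1.2 = 360.

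**3. Power on each basis** (35% versus 20%, two-sided 0.05, exact enumeration).

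| Basis | Analysed per arm | Chi-squared | Fisher |
|---|---|---|---|
| 300 as stated | 150 | 83.5% | 80.3% |
| 420 × 0.8 = 336 | 168 | 87.3% | 84.7% |
| 372 × 0.8 ≈ 298 | 149 | 83.2% | 79.9% |

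**4. Direction of the NRT assumption.** The assumed gap is 35 − 20 = 15 points, against 35 − 30 = 5 points at the cited rate. The required number analysed per arm for 80% power (chi-squared, normal approximation) is

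n = [1.96√(2p̄(1 − p̄)) + 0.842√(p₁(1 − p₁) + p₂(1 − p₂))]² / (p₁ − p₂)².

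This gives 138 at NRT 20% and 1,377 at NRT 30%. Exact power at 168 per arm, with JUUL held at 35%:

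| NRT rate | Chi-squared | Fisher |
|---|---|---|
| 20% | 87.3% | 84.7% |
| 21% | 82.0% | 78.7% |
| 25% | 51.8% | 47.2% |
| 30% | 16.6% | 13.9% |

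**The case against.** The best defence is that nothing of substance depends on the slip. The power statement at 300 analysed is correct under either test. Every explicit statement of the randomised total is 420, so the target is arguably clear and only derived figures are stale. If 420 are randomised, the text understates power. The one result below 80%, Fisher at 149 per arm, misses by 0.1 point and arises only if the true total is 372, which no section states. On the NRT rate, the plan gives a reason for going below 30%: these participants have already failed with NRT. The cited 30% also differs in time point, outcome and population.

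Much of this stands. The design is not threatened, 372 is an inference, and 20% may well be a plausible NRT rate. The power rows at 25% and 30% add information; they are not needed to repair the arithmetic. What does not stand is the sentence itself. No rounding or inflation convention reconciles it, and four derived figures in two sections point away from the stated total. Giving a reason for 20% supports its plausibility but does not make it conservative. The later remark in E.1 that the sample size is deliberately conservative is a separate statement about not counting repeated measures, and it is not at issue.

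**Conclusion.** The point holds, and the sentence is wrong as written. Against a total of 420, the per-group number is short by 24 (210 − 186) and the analysed number by 36 (336 − 300). The recruitment section is inconsistent in the same way. If 420 is the intended total, the text understates power by about 4 points (87.3% against 83.5% by chi-squared, 84.7% against 80.3% by Fisher). If 372 is intended, the Fisher test named for the comparison falls just under the claimed 80%. The derived figures look like remnants of a 372 total, but the documents do not say so, and only the sponsor can confirm which total governs. The power figures assume equal allocation, 35% versus 20%, and an analysis of completers only. The label on the NRT rate is also wrong, but it is secondary and does not drive the conclusion.

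**What to change.** Confirm the total and restate E.1 and D.2 on one basis.

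- **If 420 stands:** 420 randomised, 210 per group, 20% attrition, 336 analysed (168 per group), with power for 35% versus 20% of about 87% by chi-squared and 85% by Fisher's exact test. In the recruitment section, correct the rate to 35 per month and the share to 0.8%. This is wording only, with no extra participants, and the stated power rises.
- **If 372 is the true target:** replace 420 wherever it appears, and state 186 per group, about 298 analysed, and power of about 83% by chi-squared and just under 80% by Fisher. This is more than wording: it lowers the enrolment target by 48 (420 − 372), and the claim of more than 80% would not hold for the Fisher test.

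In either case, quote power for the test that will be used. Change *conservatively assume* to *assume*, keeping the stated reason for 20%. Add power at NRT 25% and 30%; at 336 analysed these are about 52% and 17% by chi-squared, and 47% and 14% by Fisher. The added rows cost nothing to produce, but they show openly that power falls quickly if NRT does better than 20%. Leave the remark about repeated measures as it is.

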The purpose of this 8-week phase will be to assess the effect of JUUL on product uptake and use, smoking behavior, and nicotine dependence, as well as level of toxicant exposure.. During this phase, participants will receive three OKHL coaching calls (0, +14 days, +4 weeks), complete EMAs twice a day (~120 EMAs over the phase), and complete two follow-up full assessment battery calls (0 and +8 weeks). Participants randomized to JUUL will be provided EC education, behavioral counseling, and asked to attempt to completely switch to the product for the next 8 weeks. Those randomized to NRT will be provided OKHL smoking cessation counseling and provided 8 weeks of NRT. All products to which participants will be randomized, will be provided at no cost and will be mailed to them. New cartridges will be provided based on estimated use given cigarettes per day. (see Table 2 for measures collection schedule).

Surveillance Phase

The purpose of this 4-week period is to assess how EC use evolves over time; specifically, continued use as measured by reported purchase of commercial EC product, transitions to other types or styles of ECs, smoking and other tobacco use behavior and patterns, as well as continued monitoring of iCO, a biomarker of toxicant exposure, and health effects over the 4-week period. During this phase, participants will continue to complete daily EMAs (~60) and a follow-up full assessment battery call at +12 weeks. Participants will be sent saliva collection kits if iCO is unable to be completed. Participants will not be provided ECs or NRT during this phase, but use of ECs, NRT, and other tobacco products will continue to be tracked. Also, this phase will help us to continue to track any adverse events that may occur following use of the JUUL and NRT. Those continuing to use any tobacco or EC product at the end of the surveillance phase will be advised that they can contact their state quitline and/or other local smoking cessation resources.

JUUL Education and Counseling

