All research staff will have completed Human Subjects and HIPAA training. Standard operating procedures (SOP) will be developed and all staff will be trained to ensure adherence to the SOP. Optum coaches will be trained in the delivery of the JUUL behavioral counseling and are already trained in provision of NRT and smoking cessation counseling. Training will include JUUL product safety, device features, how to use the device and troubleshooting, assessing barriers and developing switching strategies. Coach calls will be monitored and recorded to assess for fidelity (20% of calls assessed). Optum coaches all have more than 200 hours of tobacco cessation training, and thus a high degree of comfort engaging with the target population by phone. As is standard practice for our team's current studies, each assessment call/visit will have its own checklist of specific measures to be completed and the order in which they are to be administered. To reduce data entry errors, we will use secured computer-based questionnaires for research assistants to complete while completing phone-based assessments. All key on-site personnel will meet face-to-face weekly throughout the entire study. Off-site investigators will participate in these weekly meetings during the first year for project start-up; however, this will be reduced to every other week as the study progresses. During these meetings, recruitment, enrollment, data collection, data monitoring results, and any concerns or issues that may arise will be discussed.

Regulatory Issues

Reporting mechanisms: Reports to the sponsor and IRB will be made accurately and on a timely basis. These include:

- Any *unanticipated adverse device effect* occurring during an investigation will be submitted no later than 72 hours after the investigator first learns of the effect.
- *Progress reports* on the investigation will be provided at regular intervals and a copy of the report will also be sent to the study monitor. These reports include annual, interim and final NIH Research Performance Progress Report (RPPR), IRB Continuing Reviews, and any other progress reports required by NIDA.
- Any *deviation from the investigational plan* made to protect the life or physical well-being of a subject in an emergency will be reported to the sponsor and IRB as soon as possible but no later than 5 working

Switching to a Vaping Device: Evaluating Risk Reduction among Quitline Treatment Failures

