days after the emergency occurs. Except in emergency situations, prior approval will be obtained from the sponsor and IRB for any protocol change necessary to reduce risk for subjects or data quality and if the change may affect the scientific soundness of the plan or the rights, safety, or welfare of subjects, prior FDA, NIDA, and IRB approvals will be obtained as required by 21 CFR 812.150.

- Any use of the device *without obtaining informed consent* will be submitted within 5 working days after such use.
- A *final report* will be submitted within 3 months following termination or completion of the investigation or the investigator's part of the investigation. These will include Annual Progress Reports and Final Reports.
- *Any further information* requested by FDA or the IRB about any aspect of the investigation.
- *Withdrawal of IRB approval* of the investigator's part of the investigation will be reported to only the Sponsor within 5 working days of such action.
- *All changes to the protocol or DSMP (other than staffing changes)* will require approval by the NIDA Program Officer prior to implementation.
- *Serious Adverse Events* must be reported to NIDA within 72 hours.
- A *DSM report* will be sent to NIDA annually with contents to include:
 - Brief description of the trial
 - Baseline sociodemographic characteristics
 - Retention and disposition of study participants
 - Quality assurance Issues
 - Regulatory issues
 - Adverse event listing
 - Severe adverse event descriptions

Conflicts of Interest: There are no conflicts of interest to report.

3. Measures

All measures, including EMAs and iCO, have been used previously by [name] and his team. iCO, a biomarker of health and exposure, was chosen because it has shown reasonable laboratory reproducibility, has clear differences in levels between smokers and nonsmokers, demonstrate a dose-response relationship, and/or decrease upon tobacco cessation^{108,109}.

Questionnaire data will be collected over the phone or in-person by a trained research assistant and data will be entered into a secured and encrypted database using REDCap. See Table 2 for timing of measures.

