study phones at the end of the EMA period of the study. Participants will receive the final payment for completing EMAs when the study phone is received by research staff. **Bedfont iCO smokerlyzer monitor** will measure daily CO levels and biochemically confirm smoking abstinence over the course of the 3-month study. Participants will be prompted to connect the iCO device to the study smartphone each day following completion of the EMA and follow step-by-step directions to complete the CO test (see Figures 3 and 4). Results of these tests will be date and time stamped and saved. Participants will not receive feedback on test results. Our CO criteria for abstinence is consistent with numerous other studies using cutoffs of ≤ 6 ppm.¹²⁹⁻¹³⁴ As ECs do not produce CO, expired CO is a valid indicator of smoking status (i.e., switching completely to ECs) and compares favorably with cotinine and other biochemical measures that have longer detection windows.¹³⁵⁻¹³⁸ Self-reports of abstinence combined with facial recognition and CO levels suggestive of recent abstinence provide an accurate, immediate, and practical measure of abstinence. We have validated the iCO against the Vitalograph CO monitor, and our mHealth core has already integrated the iCO device into our platform. The manufacturer indicates that the iCO is valid for approximately 200 CO tests and has a sensor sensitivity of 1 ppm.¹³⁹ Our protocol will require no more than 90 CO testing sessions; well within the defined valid use range.

[figure not shown]

Figure 4. Bedfont iCO monitor completion steps.

Figure 3. Connected Bedfont iCO monitor.

Table 2. Measures

Measure	Baseline (0)	Product Trial (+8 weeks)	Surveillance (+12 weeks)	EMA ASSESSMENTS
Sociodemographic & Socioenvironment	x			Daily 90 days
Cig Dependence Scale	x			Daily Diary EMAs*
Product Use Status	x			# Cigarettes Smoked
Product Use - NRT	x			# Vaping Sessions
JUUL Use Evaluation		x	x	Other tobacco use
NRT Use Evaluation		x	x	EC product info
JUUL Expectancies – Cig		x	x	MNWS
JUUL Expectancies – Ecig		x	x	E-liquid Used
NRT Expectancies		x	x*	iCO Assessment
MNWS		x	x	Random EMAs
QSU cig		x	x	Affect/Mood/Stress
QSU ecig		x	x	Urge to Smoke
QSU NRT		x	x	Urge to Vape

Switching to a Vaping Device: Evaluating Risk Reduction among Quitline Treatment Failures

Adverse Events		x	x	Recency of Smoking
Ecig Dependence Scale		x	x	Recency of Vaping
NRT Dependence Scale		x	x	Social setting/Location
SRNT		x	x	Abstinence Self-Efficacy

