Switching to a Vaping Device: Evaluating Risk Reduction among Quitline Treatment Failures

Aim 1: The focus of aim 1 is the examination of differential levels of (Hyp 1a) substitution between JUUL and NRT, and (Hyp 1b) reported nicotine craving, withdrawal symptoms, number of cigarettes smoked per day, product abuse liability, and nicotine dependence, between JUUL and NRT. *Hypothesis 1a:* Complete substitution rates, at the 8 and 12 week follow-ups, will be compared between JUUL and NRT arms using logistic regression analysis, adjusting for baseline variables such as age, gender, number of cigarettes per day and/or randomization stratification factors. The GEE model will be performed for the repeated measure analysis of complete substitution rate across multiple visits. *Hypothesis 1b:* If needed, we will apply a normalizing transformation to the response measure (e.g., taking the logarithm of cigarettes per day) before proceeding with the analysis, as a means of removing the effects of potential outliers. We will examine changes in each outcome over time across the two groups using linear mixed model (LMM) regression analysis. We will employ a random intercept or slope parameter, as appropriate, and model the covariance structure for the repeated outcome measures, while accounting for baseline value of the outcome and potential confounders (including any variables not equally distributed between groups). Modeling is done using a likelihood-based approach and thus makes use of all available data (on the intention-to-treat (ITT) sample) to produce consistent estimates of the regression parameters. Contrast estimates comparing group effects over time will be used as measure of effect. A similar approach will be used to explore the EMA data collected.

Aim 2: The focus of aim 2 is the examination of changes in a biomarker of toxicant exposure. *Hypothesis 2:* We will examine changes in iCO, a biomarker of toxicant exposure, and EMA data using the methods outlined in Hypothesis.

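### Table 2 contradicts the baseline-adjusted Hyp 1b model for four instruments: three have no baseline mark, and the Cigarette Dependence Scale has no follow-up mark

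*Combined protocol and SAP*

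**What the plan says.** Section E.2, Aim 1, lists the Hyp 1b outcomes as craving, withdrawal, cigarettes per day, abuse liability and nicotine dependence. The analysis is stated as follows: "We will examine changes in each outcome over time across the two groups using linear mixed model (LMM) regression analysis". The model is to be fitted "while accounting for baseline value of the outcome and potential confounders".

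Three places in the prose put a battery at time 0. D.1 (Design Overview) gives batteries at 0, +8 and +12 weeks. D.2 (Baseline and Follow-up Assessments) has a baseline battery finished before randomization. The D.2 text on the product trial phase says participants will "complete two follow-up full assessment battery calls (0 and +8 weeks". None of the three says which instruments the time-0 battery contains.

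For that content the protocol defers to Table 2. The product trial phase text says "see Table 2 for measures collection schedule", and D.3 says "See Table 2 for timing of measures". In Table 2, MNWS, QSU cig and Cigarette Purchase Task are marked at +8 and +12 weeks with the baseline cell empty. The row "Cig Dependence Scale" is marked at baseline with both follow-up cells empty.

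**The concern.** A model that adjusts for the baseline value of an outcome, or estimates change from baseline, needs that value for each participant before randomization. Under Table 2 it does not exist for visit-based withdrawal, cigarette craving or the purchase task. For cigarette dependence the gap runs the other way: there is a baseline value and nothing to compare it with.

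The table may well govern what is collected, because the Quality Assurance text says "each assessment call/visit will have its own checklist of specific measures to be completed". If those checklists are built from Table 2, the baseline values are never taken, and a pre-randomization value cannot be recovered later. E.2 also does not say which of the cigarette, e-cigarette and NRT dependence scales tests the dependence part of Hyp 1b, so the plan does not show how that part would be analysed.

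**Working it through.** The plan gives no power or precision figure for Hyp 1b (its power statement concerns complete substitution only), so there is no figure to reproduce. The check compares the schedule with what the model needs.

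**Step 1. Schedule against model.** Marks are from Table 2; the outcomes are those listed in E.2 and measured as described in D.3.

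| Table 2 row | Hyp 1b outcome | 0 | +8 | +12 | Baseline-adjusted model | Unadjusted arm contrast |
|---|---|---|---|---|---|---|
| MNWS | withdrawal | – | x | x | not possible | possible |
| QSU cig | craving | – | x | x | not possible | possible |
| Cigarette Purchase Task | abuse liability | – | x | x | not possible | possible |
| Cig Dependence Scale | dependence | x | – | – | not possible | not possible |

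**Step 2. Can the daily EMA data supply a baseline?** The EMA list includes MNWS and urge items. But the phones are mailed (D.3), randomization follows the baseline assessment at once (D.2, Baseline Phase), and no EMA period before randomization is described. The first EMA values are therefore post-randomization and are not a true baseline. The purchase task and the dependence scales are not in the EMA list.

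**Step 3. Is cigarettes per day affected?** No. D.2 uses the baseline smoking rate to allocate product, and E.2 names cigarettes per day among the baseline covariates. Follow-up values come from the daily diary and the TLFB row.

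**Step 4. What the missing baseline costs in precision.** The documents give no baseline-to-follow-up correlation r, so a range is assumed. For a contrast at one visit:

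adjusted variance / unadjusted variance = 1 − r²

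- r = 0.3: 1 − 0.09 = 0.91
- r = 0.5: 1 − 0.25 = 0.75
- r = 0.7: 1 − 0.49 = 0.51

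The matching standard-error ratios (square roots) are 0.95, 0.87 and 0.71. The gain is smaller if other baseline covariates, such as cigarettes per day, already explain part of the outcome. These are illustrations, not the plan's detectable differences.

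**The case against.** The strongest reply is that the table is mis-marked and the data will be collected. Three prose passages and the E.2 model all point to a battery at time 0. Table 2 is also not a complete inventory: D.3 describes a Drug Effects/Liking Questionnaire that has no row under that name, and it places expectancies in the tobacco use history while Table 2 shows them at follow-up only. An empty cell is therefore weak evidence that a measure will not be taken. This stands, and it is why the finding is conditional. It does not remove the contradiction: the prose names no instruments and sends the reader to the table.

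A second reply is that randomization protects the arm comparison at +8 and +12 weeks without a baseline term. That is correct for the three follow-up-only instruments. It does not help the Cigarette Dependence Scale, which has no follow-up value.

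A third is that the Cigarette Dependence Scale may not be the right construct, since Hyp 1b predicts higher perceived nicotine dependence with JUUL. That also stands. It is a reason to name the scale, not to leave the question open.

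A reader might go further. None of the 21 visit rows in Table 2 is marked at both baseline and follow-up (4 are baseline only, 17 follow-up only), and one could infer that the change analyses fail throughout. The documents do not support that. Many of the 17 rows are specific to a study product or arise only after exposure: product use evaluations, e-cigarette and NRT urges and dependence, and adverse events. Recent daily e-cigarette users are excluded, so a baseline e-cigarette dependence score would mean little for most participants. Sociodemographic items need no repeat.

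Nor is Aim 2 left without an analysis. Its method statement breaks off at "using the methods outlined in Hypothesis", but this reads as a dropped label, most naturally for the Hyp 1b model. The iCO monitor is used daily for 12 weeks (about 84 readings per participant), so a trajectory can be modelled.

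**Conclusion.** The point holds as an internal inconsistency over four Table 2 rows. It rests on one assumption that the documents do not settle: that the call checklists follow Table 2. If they do, the Hyp 1b model as written cannot be fitted for visit-based withdrawal, cigarette craving and the purchase task, and cigarette dependence has no arm comparison after randomization, adjusted or not. If they follow the prose instead, the fault is an error in the table.

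The size is modest. For three secondary outcomes, what is lost is precision (adjusted variance 0.91 to 0.51 of unadjusted, at assumed r of 0.3 to 0.7) and the estimate of change from baseline. For the fourth, the follow-up itself is lost. The primary outcome, cigarettes per day, the EMA and daily iCO trajectory models, and unadjusted contrasts for outcomes measured at +8 and +12 weeks are not affected. It should be fixed because uncollected baseline values cannot be replaced and the remedy is cheap.

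**What to change.** Reconcile Table 2 with D.1, D.2 and E.2:

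1. Mark MNWS, QSU cig and Cigarette Purchase Task at the pre-randomization baseline.
2. Mark the Cigarette Dependence Scale at +8 and +12 weeks.
3. In E.2, name the scale that tests the dependence part of Hyp 1b. If it is a product-specific scale with no meaningful baseline, state that its model has no baseline term.
4. Check that the call checklists match the amended table.

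All four instruments are already in the study and all three assessments are already scheduled. The cost is a table amendment, a sentence or two in the analysis plan, and a little more participant time at each assessment. Items 1 and 2 help only participants who have not yet reached the assessment concerned. For anyone randomized without a baseline value, the plan should say how the model handles its absence.
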